6.3 Pre-procedure tests and process

6.3.1. Prior to randomization

- Detailed history and physical examination, checking for inclusion and exclusion criteria, baseline GCSI score, PAGI-SYM and score. There is no washout period for prokinetics or antiemetics prior to G-POEM (allowed drugs). All prokinetics should be discontinued at least 48 72 h before gastric emptying study. Patients with a previous attempt(s) of pyloric balloon dilatation, temporary stenting or botulinum toxin injection are eligible for inclusion, but there must be a wash-out period of at least 6 months prior to randomization.
 - Upper GI endoscopy with gastric and duodenal biopsies (diagnosis of *H. pylori* and exclusion of eosinophilic gastroenteritis) (less than 4 months prior to randomization). In patients tested positive for H.pylori, its treatment will be discussed with the patient individually. Treatment of H.pylori is not necessary before enrolment unless there is an absolute indication for its treatment.
 - Gastric emptying study (**Appendix 3**): scintigraphy protocol in all patients (protocol endorsed by ANMS: American Nuclear Medicine Society, 2009); (less than 6 months prior to randomization). Test will begin with patients under fasting conditions for a minimum of 6 hours. A radiolabelled meal will be prepared by adding 0.75 mCi ^{99m}Tc-sulfur colloid into 2 the liquid egg whites. Eggs will be cooked in a microwave or on a hot nonstick skillet, the egges will be stirred once or twice during cooking until firm to the consistency of an omelette. Then, the bread will be toasted and jelly spread on the toasted bread. Gamma camera images will be obtained immediately after meal ingestion and then at 1, 2, 3 and 4 hours. The geometric mean of delay-corrected counts will be used to estimate the proportion of ^{99m}Tc emptied at each time point. Diagnostic criterion for gastroparesis is defined as the percentage of gastric retention >60% at 2 h and equal to or greater than 10% at 4 h or both. Half-time (T1/2) emptying time will also be calculated. In case of poor tolerance of solids during gastric scintigraphy, radiolabelled liquids will be used (see inclusion criteria). At least 72 hours before gastric emptying test, narcotics and other medications that can delay gastric emptying should be discontinued.

Other alternative meals may be used for patients with egg allergies or egg's intolerance according to the local principles.

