Follow up visits are scheduled at 3 and at 6 months. At 6 months, all patients will be informed about their treatment allocation and patients in the sham group will be offered G-POEM in case of their persisting symptomatology (no or minor benefit of the sham procedure). The decision must be made in next 3 months and these patients undergo the G-POEM procedure no longer than 6 months after the previous follow-up visit. Further follow-up visits for patients randomized to the active arm are scheduled at 12M, 24M and 36M.

Patients originally randomized into the sham arm, who will undergo G-POEM, will be followed like patients after G-POEM (f-u visits at 3M, 6M, 12M, 24M and 36M) (**Appendix 6**) except of scintigraphy/GEBT at 12M (Table 8B).

Patients originally randomized into the sham arm who had treatment success or didn't want to undergo G-POEM will be followed at 12M and 24M to be sure there is none treatment recurence.

For both, active and SHAM groups, diet modification, nutrition support, prokinetics, antiemetics are allowed during the follow-up. No interventions such as pyloric balloon dilatations, transpyloric stent placement, botox application or surgery) are allowed during the follow-up.

Unscheduled visits or telephone contacts may occur as needed. No time windows or minimum time separations are imposed for such visits or contacts. Data collection forms are not required at interim visits. If gastroparesis symptom exacerbation occurs between scheduled visits, complete the Interim Event Report (IE) form. The visit code for the form will be "n" (not applicable in this situation)

3M visit (±3 weeks):

- Symptom questionnaires (PAGI-QoL, GSCI, PAGI-SYM)
- Body weight/BMI
- Endoscopy
- Gastric emptying study (scintigraphy) in all pts
- Gastric emptying breath test (optional)
- EndoFLIP measurement (only after G-POEM, may be performed 3-9 months after G-POEM), patients from sham group will undergo the "sham EndoFLIP measurement"

6M visit (± 1 month):

- Symptom questionnaires (PAGI-QoL, GSCI, PAGI-SYM)
- Body weight/BMI

12M visit (± 1 month):

- Symptom questionnaires (PAGI-QoL, GSCI, PAGI-SYM)
- Body weight/BMI
- Endoscopy (optional)
- Gastric emptying study (scintigraphy) in the active arm only (Tab. 8A)
- Gastric emptying breath test (optional)
- No GES (scintigraphy) in the sham group after unblinded allocation to G-POEM (Tab. 8B)

24M and 36M visit (±2 months):

- Symptom questionnaires (PAGI-QoL, GSCI, PAGI-SYM)
- Body weight/BMI

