- Gastric emptying study (scintigraphy) at 36M (optional)

Table 8A – study design for patients in the active (G-POEM) group

		Patients in G-POEM group at the beginning of randomisation										
		Baseline	POD 0 – day of GPOEM	POD 1	3M	6M	12M	24M	36M			
Scinti / GE	BT	•			•	1	•		(optional)			
Endoscop	у	•	•	(optional)	•	-	(optional)					
GCSI + PA SYM + PA QoL	_	•			•	•	•	•	•			
Blood test	ts	•		•								
EndoFLIP			Before and after GPOEM		③							

GEBT (Gastric emptying breath test), QoL = Quality of Life, GCSI = Gastroparesis Cardinal Symptoms Index, PAGI-SYM = Patient Assessment of Upper Gastrointestinal Disorders Symptoms, PAGI-QoL = Patient Assessment of Upper Gastrointestinal Disorders-Quality of Life, POD - Post Operative Day.

Table 8B – study design for patients randomized in the sham group

		Patients in sham group / allocation to G-POEM procedure*											
	Baseli ne	POD 0	POD 1	3M	6M *	POD 0/ G-POEM	POD1	3M	6M	12M	24M	36M	
Scinti / GEBT	•			•	-			•				(optional	
Endoscopy	•	•	(optional)	•	-		(optional)	•		(optional)			
GCSI + PAGI-SYM + QoL, PAGI- QoL	•			•	•			•	•	•	•	•	
Blood tests	•		•				•						
EndoFLIP		⊕ Before [⊥]		Sham		After GPOEM		③					

^{*} At 6M, the patients in sham arm will be offered to undergo G-POEM (if their symptoms persist).

*In patients having undergone EndoFLIP during the sham procedure, no EndoFLIP measurement will be repeated prior to G-POEM.

♦ sham measurement

10. Study outcomes

a. Main outcome

Main outcome is the proportion of patients with treatment success at 6 months after the procedure.

Treatment success is defined as a decrease of a total GSCI symptom score at least **50%** (see Table 9 for GSCI values to define treatment success according to a baseline GSCI value).

Table 9: GSCI values to define treatment success according to the baseline GSCI value

Mean GCSI score total – baseline	Maximal GSCI score for treatment success (decrease of GSCI about 50%)
2.31*	1.15
2.4	1.20
2.5	1.25
2.6	1.30
2.7	1.35
2.8	1.40
2.9	1.45
3.0	1.50
3.1	1.55 (see description below the table)
3.2	1.60
3.3	1.65
3.4	1.70
3.5	1.75
3.6	1.80
3.7	1.85
3.8	1.90
3.9	1.95
4.0	2.00
4.1	2.05
4.2	2.10
4.3	2.15
4.4	2.20
4.5	2.25
4.6	2.30
4.7	2.35
4.8	2.40
4.9	2.45
5.0	2.50

NOTE: GSCI above 2.3 is an inclusion criterion

Example: If baseline GSCI value was 3.1, a patient will have treatment success if post-treatment GSCI score will be 1.55 or lower.

10.2. Secondary outcomes:

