- 1. Proportion of patients with treatment success in the active arm at 3M, 12M, 24M and 36M.
- 2. Proportion of patients with treatment success in the sham group at 3M.
- **3.** Change in GSCI and PAGI-SYM before and after G-POEM at 3, 6, 12, 24 and 36M and before vs. after sham procedure at 3M and 6M; comparison of the change of the scores between the active and sham groups.
- **4.** Proportion of patients (randomized into the sham group and undergoing G-POEM after 6M) with treatment success after the sham procedure (6M) and after G-POEM (6M) cross over part
- **5.** Change in GSCI and PAGI-SYM before and after G-POEM vs. sham procedure in patients randomized to the sham group at 3 and 6M (cross over part)
- 6. Subgroup post-hoc analyses of the treatment success and change in symptomatic scores according to etiology of gastroparesis.
- 7. Change in gastric emptying (scintigraphy) study, EndoFLIP values and/or gastric emptying breath test before and after both G-POEM and sham procedure; comparison of the mean change of these parameters between active and sham groups.
- **8.** Procedure details (length of the procedure, technical success, perioperative adverse events).
- 9. Short- and long-term adverse events.

11. Sample size calculation

A total of 86 patients will be randomized.

- 43 patients will be randomized into the G-POEM group
- 43 patients will be randomized into sham group

Sample size calculation is based on expected therapeutic success of G-POEM in 50% of patients vs. 20% in the sham group; significance level 0,05; study power 0,8; beta error 0,2; adjustment for 15% expected drop out.

12. Statistical analysis

Data will be analyzed for both the intention to treat (ITT – a cohort for primary end point analysis) and the per-protocol population (sensitivity analysis). The per-protocol analysis will include only patients who will complete the entire follow-up. The efficacy of G-POEM at month 6 (main outcome) will be evaluated by Poisson regression with robust standard errors or similar regresion based approach. Baseline characteristics will be compared by using chi-squared tests for categorical variables and t-tests for continuous data.

The efficacy of treatment at other time points (3M, 12M, 24M and 36M) as well as the pooled efficacy cross-over + active groups will be evaluated similarly.

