Appendix 8:

Adverse event (AE) / Serious Adverse Event (SAE) Report Form

Definition: An adverse event is any undesirable, unintentional or unanticipated event that occurs during use of the investigational device, whether or not considered related to the therapy. A serious adverse event (SAE) is an event that is: fatal, life-threatening, results in persistent or significant disability/incapacity, requires or prolongs inpatient hospitalization. SAE must be reported within 24 hours to the Prague study center ([contact], copy: [contact]) and the Ethics Committees/IRB if applicable.

Hospital visits due to follow up visi	ts are not conside	ered to be SAE.	
☐ Initial report			
□ Consecutive report			
Date AE start:///		unexpected event	
Event related to G-POEM / SHAM $\hfill \square$ No	procedure □ Possibly		□ Yes
Complication: □ Perforation	□ Bleeding	□ Infection	□ Other
Please describe complication:			
Intervention required: No please describe intervention:		Yes	
medication required: No medication(s):		Yes	

R	eport	tof	a	Ser	ious	Ad	lvers	se E	lven	t
---	-------	-----	---	-----	------	----	-------	------	------	---

Hospitalization or prolongation	of nospital stay red Yes	uired (SAE): □ No	
If yes, please report within 24 happlicable!	ours to the Prague	e study center and Ethics Committee/IRB	if
Date of hospitalisation/ - prolon	gation(I	DDMMYY)	
Date hospital discharge	(DDMMYY)		
□ event resolved	□ event ongoi	ng	
□ long term sequela	□death	□ unknown	
Description/ comment:			
Date AE ston: / /	(DDMMYY)	

Data and Safety Monitoring Board

IKEM, Department of hepatogastroenterology 8th of February 2021, Prague

Study: A Randomized, Sham and Cross-Over-Controlled Trial of per-oral endoscopic pyloromyotomy (G-POEM) in patients with refractory gastroparesis (GREG)

ClinicalTrials.gov identifier: NCT03356067

Grant number: 17-28797A

To the principal investigator

[name]
Department of hepatogastroenterology
IKEM
[name]

The DSMB met at 29th of January 2021 and reviewed interim results after 41 subjects have been randomized and 33 patients completed the M6 visit. At present, there is a significant difference regarding the main endpoint (treatment success at 6 months) in favor of the active group (vs. sham). Also, 100 % of patients, who had undergone cross-over G-POEM after they underwent a sham procedure, experienced a treatment success. Based on these results, the Committee recommends to stop enrolment now because:

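### No GCSI or PAGI-SYM is scheduled at the time of the cross-over G-POEM, and the protocol does not say which baseline defines cross-over success and change

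*Protocol*

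**What the plan says.** **Timing of the cross-over (section 9.d).** At 6 months all patients learn their allocation, and sham patients who had little or no benefit are offered G-POEM. They have 3 months to decide. On the date of the procedure itself, the section says that "these patients undergo the G-POEM procedure no longer than 6 months after the previous follow-up visit".

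**What is measured before it.** In Table 8B the row for GCSI, PAGI-SYM and quality of life is marked at baseline, sham 3M and sham 6M. It is blank at the cross-over procedure and resumes 3 months after it. The scintigraphy/breath-test row is marked at baseline and sham 3M and is also blank at the cross-over procedure. For EndoFLIP, a footnote says that "no EndoFLIP measurement will be repeated prior to G-POEM" when it was done during sham. Section 9.d lists questionnaires and weight at 6M, with no emptying test. Appendix 5 lists weight, quality of life, ASA status and blood tests for the day before G-POEM, but neither symptom score.

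**What the outcomes need (section 10.2).** Outcome 4 is treatment success after sham and after the later G-POEM in the same patients. Outcome 5 is "Change in GSCI and PAGI-SYM before and after G-POEM vs. sham procedure in patients randomized to the sham group at 3 and 6M". Section 12 adds success rates for the cross-over group and for original and cross-over G-POEM patients pooled.

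**What success means (section 10.a, Table 9).** Success is a fall of at least 50% in total GCSI from baseline. No separate baseline is defined for the cross-over.

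**The concern.** A before-and-after comparison needs a value close to the intervention. Here the value before it can come from a visit half a year earlier, and in between the patient knows that the first procedure was sham. Diet changes, prokinetics and antiemetics are all permitted in that time. PAGI-SYM looks back only 2 weeks (section 6.2.2), and GCSI is part of it (section 3), so a 6M score says little about symptoms at the procedure. Drift could go either way, and no measurement exists to show which.

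The second problem is the denominator of the 50% rule. A cross-over patient has at least two candidate baselines, the enrolment score and the sham 6M score. If the enrolment score is used, any improvement after sham is credited to G-POEM. If the 6M score is used, the criterion differs from the one applied to the active arm, with which these patients are to be pooled. An analysis plan written later could choose between these two scores, but it could not recover an admission score that was never collected.

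**Working it through.** The protocol gives no figure for the age of the values before cross-over. It follows from the visit schedule.

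**Inputs.** Sham 3M visit, window ±3 weeks; sham 6M visit, window ±1 month; cross-over G-POEM up to 6 months after the 6M visit (all section 9.d). Three weeks = 21/30.4375 = 0.69 months.

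**Age of the last value at a G-POEM done at the 6-month limit**

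- Latest G-POEM at nominal visits: 6 + 6 = month 12 after sham. With a late 6M visit: 7 + 6 = month 13.
- GCSI and PAGI-SYM from sham 6M: 12 − 6 = 6 months. The limit runs from that visit, so the window does not change it.
- Scintigraphy from sham 3M, nominal: 12 − 3 = 9 months.
- Scintigraphy from sham 3M, extreme windows: 13 − (3 − 0.69) = 10.7 months.

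For comparison, section 6.3.1 requires the entry scintigraphy to be "less than 6 months prior to randomization". That is an eligibility limit and not an analysis rule, but it shows how recent a test the protocol wanted at entry. All these ages are maxima; the document reports no actual intervals.

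**Effect of the choice of baseline.** Success threshold = 0.5 × baseline GCSI. For a baseline of 3.5 this gives 0.5 × 3.5 = 1.75, which matches the row in Table 9. The GCSI values below are assumed, and show a small and a larger improvement after sham:

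| Enrolment | Sham 6M | Fall after sham | Threshold from enrolment | Threshold from sham 6M | Fall from sham 6M that suffices if enrolment is the baseline |
|---|---|---|---|---|---|
| 3.5 | 3.15 | 10% | 1.75 | 1.575 | (3.15 − 1.75)/3.15 = 44% |
| 3.5 | 2.4 | 31% | 1.75 | 1.20 | (2.4 − 1.75)/2.4 = 27% |

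A patient scoring 1.6 six months after the cross-over G-POEM is a success against enrolment in both rows (1.6 ≤ 1.75). Against sham 6M the same patient is a failure in both (1.6 > 1.575 and 1.6 > 1.20). The range of scores that changes class is 1.75 − 1.575 = 0.175 points wide in the first row and 1.75 − 1.20 = 0.55 in the second.

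**The case against.** Much can be said on the other side, and several parts of it stand.

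- **There is a score before the cross-over.** GCSI and PAGI-SYM are measured at sham 6M, the visit at which G-POEM is offered. What is missing is an assessment at the procedure itself. Appendix 5 already lists quality of life for the day before G-POEM, so that measure needs no addition.
- **Table 9 points to enrolment.** It starts at 2.31 and repeats the entry criterion in its note, and Table 8B has a single baseline column. For success this is the more natural reading, but no sentence says so for the cross-over. Table 9 also does not settle the before-value for the change in outcome 5.
- **Gastric emptying and EndoFLIP.** A reader might infer that outcome 7 fails for lack of a fresh test. The comparison it states is active versus sham, which the randomized baseline and 3M scintigraphy support. Reusing the sham EndoFLIP value is an explicit design choice. Scintigraphy age matters only if a cross-over emptying change is reported.
- **The larger gap needs a sizeable sham response.** Cross-over is meant for patients with little or no benefit, so the 10% row may be more typical. Section 9.d sets no GCSI limit, however, so the 31% row is not excluded.
- **The monitoring board's recommendation.** The DSMB report mentions that "100 % of patients, who had undergone cross-over G-POEM after they underwent a sham procedure, experienced a treatment success", and a reader might infer that a poorly defined baseline drove the decision to stop enrolment. The documents do not support that. The board's numbered reasons are the randomized comparison (p = 0.003) and the ethics of anaesthesia for sham. Nothing shows that the 100% depends on the choice of baseline.
- **An admission score has its own bias.** It is given by a patient who knows that the first procedure was sham and expects active treatment. This argues against making it the sole main baseline, but not against collecting it.

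**Conclusion.** The point holds as a limited one. No GCSI or PAGI-SYM is scheduled at the cross-over G-POEM, the last scores can be 6 months old, and the baseline for cross-over success and change is not named. Outcome 5 therefore cannot separate the effect of G-POEM from drift during an unblinded wait. Outcome 4 and the pooled rates can classify the same patient differently depending on the baseline chosen.

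Table 8B was read from a converted file, but the visit lists in section 9.d and Appendix 5 agree with it. The ages assume a G-POEM at the permitted limit, and the thresholds assume the GCSI values shown. How many patients would change class cannot be known from the document.

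It would be wrong to infer that the main result is in doubt. Section 12 makes the randomized 6-month comparison the only confirmatory test, and everything affected here is exploratory. The primary analysis and the sample size of 86 do not depend on it. This is an inexpensive improvement, not a defect in the primary design.

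**What to change.** 1. Add GCSI and PAGI-SYM to the cross-over procedure column of Table 8B, completed at the existing admission before G-POEM.
2. State one baseline for outcomes 4 and 5 and for the pooled success rates. Report success and change against the other available baselines (enrolment, sham 6M, admission) as sensitivity results.
3. If a cross-over change in gastric emptying is reported, give the age of the preceding scintigraphy alongside it. Do not exclude patients by that age, which would select on waiting time in a small group.

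The cost is one extra pair of questionnaires per cross-over patient, with a change to Table 8B and a sentence or two in sections 10 and 12. The admission score may be affected by expectation after unblinding, which is why the enrolment and sham 6M results should stand beside it. For patients already crossed over without an admission score, only those two baselines are available, and naming the main one still helps.

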6.3.2. Randomization

Patients fulfilling all inclusion criteria (and without exclusion criteria) will be asked to sign an informed consent form. Then, participants will be randomly allocated into the two groups:

- A. Group that will receive G-POEM (active arm), or
- B. Group that will receive sham procedure ("placebo" arm)

The patients will be stratified by the etiology of gastroparesis and gender. Patients will be randomised in blocks of 6. After signing an informed consent form, each centre will e-mail patient initials, birth date, patient's gender and etiology of gastroparesis (1= idiopathic or other, 2= diabetic; 3 = post-surgical) to a study nurse in Prague and she will send back as soon as possible the treatment allocation with patient's number. Patients will be randomized in 1:1 allocation ratio and patients must not be informed about their assignment.

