6.3.3. Post-randomization tests (before the procedure)

- PAGI QoL (appendix 4)
- Body weight/BMI, ASA physical status
- Current lab values (Haemoglobin, WBC, RBC, Thrombocytes, CRP, Quick, Haemoglobin A1c in patients with DM)
- Upper GI endoscopy 1 day prior to the procedure (optional for removing food residues)
- EndoFLIP measurement of pyloric distensibility, cross-sectional area and diameter
 under general anesthesia before G-POEM/sham

Patients will be admitted to the hospital one day prior to the procedure or the day of the procedure. The day before the procedure, patients will be allowed to drink until 20.00. In the morning (day of the procedure), proton pump inhibitor (PPI) (e.g. omeprazole 40 mg) will be administered intravenously to patients allocated to the active (G-POEM) group; patients in the sham arm will be given placebo (normal saline) (**Appendix 5**).

7. EndoFLIP

EndoFLIP (= Functional Lumen Imaging Probe) is a new method using a principle of impedance planimetry allowing to measure distensibility of a hollow organ, ideally sphincter. In the stomach, it could help to understand the contributing pathophysiology of an impaired function of a pyloric sphincter in patients with gastroparesis. Furthermore, it could help to select appropriate patients for pylorus-directed therapies in patients with gastroparesis, as EndoFLIP provides real-time and dynamic information on pyloric distention, cross-sectional area and diameter.

EndoFLIP measurement will be performed three times: before the procedure (during sham procedure or just before G-POEM), immediately after G-POEM and 3-9 months after G-POEM, always in sedated patients (3-9 months) or in patients under general anesthesia (prior to and after G-POEM). After the calibration, the balloon, equipped with pressure and impedance sensors, will be introduced into the esophagus and under endoscopic control will be passed through the pylorus into the correct position. If necessary, special accessories (snare, grasper) will be used. After that, measurement of various parameters will be performed and the following values will be recorded: distensibility, balloon pressure, cross sectional area, diameter under different balloon volumes (30, 40 and 50 mL). EndoFLIP procedure prolongs the endoscopic examination by approximately 10-15 minutes.

G-POEM procedure

The procedure consists of the following steps (Table 5):

Table 5:

- 1) Mucosal incision at the greater curvature 3-5 cm from the pylorus

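### EndoFLIP timing is not matched between the arms before the 6-month endpoint, so some G-POEM patients may be able to infer their allocation

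*Protocol*

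**What the plan says.** Section 7 (EndoFLIP) schedules the measurement before the procedure, then "immediately after G-POEM and 3-9 months after G-POEM", with the late measurement made under sedation. The 3M visit list in Section 9d repeats the window and adds a mock for the other arm: "EndoFLIP measurement (only after G-POEM, may be performed 3-9 months after G-POEM), patients from sham group will undergo the" mock measurement. No window is written for the mock.

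The schedule tables point to 3M. "Table 8A – study design for patients in the active (G-POEM) group" marks one follow-up EndoFLIP, apparently in the 3M column (the extracted table is imperfect), and does not show the 3-9 month window. "Table 8B – study design for patients randomized in the sham group" puts the mock in the 3M column before crossover. Both tables have an endoscopy at 3M and none at 6M.

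On blinding, Section 6.3.2 says that "patients must not be informed about their assignment", and Section 8 asks staff not to disclose it. Section 8 also says in general terms that the remaining tests after the sham procedure should be handled as in the G-POEM arm. Section 9d ends the blind: "At 6 months, all patients will be informed about their treatment allocation".

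The main outcome (Section 10a) is a fall of at least 50% in total GCSI at 6 months. The analysis plan in Section 12 names this comparison as the study's only confirmatory test.

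**The concern.** A mock EndoFLIP is useful only while the patient is blinded, which means before disclosure at 6M. It works only if both arms go through the same thing in that period. As written, every sham patient has a mock at 3M, while a G-POEM patient may have nothing at 3M and a real measurement later.

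That leaves two possible cues, both pointing to G-POEM: no measurement at 3M, or a separate sedated examination between the 3M and 6M visits.

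The patient is both the blinded party and the rater of the endpoint. The Study Summary gives a possible placebo effect as the reason for the sham control. If some active patients infer their arm and report better scores, the bias favours G-POEM on the one test that carries the conclusion. The measurement that creates the cue serves only an exploratory outcome (secondary outcome 7).

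**Working it through.** **1. The timing rules side by side**

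| | G-POEM arm | Sham arm, before crossover |
|---|---|---|
| Section 7 | 3-9 months after G-POEM, sedated | no follow-up timing given |
| Section 9d, 3M visit (±3 weeks) | may be done at 3-9 months | mock, no window stated |
| Tables 8A / 8B | one mark, apparently 3M | mock at 3M |
| Mock at 3M if the real one is deferred | not provided for | not applicable |

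The 3-9 month window lasts 6 months, about 26 weeks. The first 3 weeks fall inside the 3M visit window. About 13 - 3 = 10 weeks lie between the end of that window and 6M, and about 13 weeks lie after 6M. Most of the permitted window is therefore outside the visit at which the mock is listed. This describes what is allowed, not what sites do.

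**2. The plan's own figure**

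Section 11 gives 50% against 20% success, alpha 0.05, power 0.80 and 15% dropout. Taking alpha as two-sided (not stated) with unpooled variance:

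n = (0.50×0.50 + 0.20×0.80) × (1.960 + 0.842)² / 0.30² = 35.76, so 36 per arm.

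36 / (1 - 0.15) = 42.4, so 43 per arm and 86 in total. The stated 86 is reproduced, and this point does not change it. It supplies only the 43 per arm and the 20% used below.

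**3. Illustration of size (assumed bias, not estimated)**

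The documents give no deferral rate, no rate at which patients would notice, and no size of reporting bias. Assume:
- true success of 20% in both arms;
- 43 per arm, because the primary analysis is ITT with multiple imputation;
- a share f of active patients who are deferred and infer their allocation;
- a rise b in the success rate those patients report.

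The observed active rate is p₁ = 0.20 + f×b. With d = p₁ - 0.20, p̄ = (p₁ + 0.20)/2, SE₀ = √(2p̄(1-p̄)/43) and SE₁ = √((p₁(1-p₁) + 0.16)/43), the two-sided rejection rate is

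Φ((d - 1.96·SE₀)/SE₁) + Φ((-d - 1.96·SE₀)/SE₁).

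Worked case, f = 0.5 and b = 0.20: p₁ = 0.30, SE₀ = 0.0934, SE₁ = 0.0928. The first term is Φ((0.10 - 0.183)/0.0928) = 0.185 and the second is 0.001, giving 0.186.

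| f | b = 10 points | b = 20 points | b = 30 points |
|---|---|---|---|
| 10% | 5.1% | 5.6% | 6.3% |
| 25% | 5.9% | 8.6% | 12.8% |
| 50% | 8.6% | 18.6% | 34.2% |

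As a cross-check, exact enumeration of a pooled two-proportion test with 43 per arm gives rejection in favour of G-POEM of 2.6% with no bias, and 8.3%, 19.1% and 35.0% when the active rate rises by 5, 10 and 15 points. With 36 per arm the figures are 2.5%, 7.1%, 16.0% and 29.9%. The pattern is the same.

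**The case against.** **The mock is not fixed at 3M.** The tables show 3M as the default in both arms, real and mock share one bullet in Section 9d, nothing forbids flexibility in the sham arm, and Section 8 asks for like handling of tests. All of this is true. But the Section 8 sentence is general, while Section 9d is specific and writes the window for G-POEM only. Giving the sham arm the same 3-9 months would not settle it, because a mock after the 6M disclosure protects nothing. And no section provides a mock at 3M for an active patient whose real measurement is deferred.

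**Patients may not notice.** A reader might infer that any patient without a 3M measurement is thereby identified as active. The documents do not support that. Both arms have a 3M endoscopy, EndoFLIP adds only about 10-15 minutes, and the follow-up measurement is made under sedation. The patient would have to notice the omission and also know how the schedule differs by arm. What patients are told about this is not in the text available, and the protocol does not say whether the 3M endoscopy is sedated without EndoFLIP. A patient told to expect a measurement at some time from 3 to 9 months would learn little from its absence at 3M. A separate sedated examination before 6M is easier to notice. What stands is a possible cue, not identification.

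**Balloon distension as a one-arm treatment.** A reader might also infer that a real distension of the pylorus in active patients before 6M adds an intervention that the sham arm lacks. Nothing in the protocol says that EndoFLIP affects symptoms. It is scheduled as a measurement, while Section 9d separately bars balloon dilatation, and sham patients have a real EndoFLIP during the sham procedure. That reading is not part of this point.

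**The error rates are assumed.** This is correct. They show what a given bias would do to the test, and they do not measure this defect.

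**Conclusion.** The point holds as a gap in the protection of the blind. Sections 7 and 9d let the timing of the real measurement move in one arm, the mock is listed only at 3M, and the general wording in Section 8 does not close the gap. Some G-POEM patients may therefore be able to infer their allocation before the 6M GCSI.

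Its size cannot be derived from the protocol. Under the assumptions shown, the two-sided error rate stays near the nominal 5% if deferral is rare (5.1-6.3% at 10%) and becomes material if it is common (8.6-34.2% at 50%). These ranges assume that the deferred patients infer their arm and report 10 to 30 points more success. The documents do not show that any patient was unblinded this way. The case for changing the text is that the risk is avoidable at small cost and bears on the only confirmatory, patient-reported endpoint.

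**What to change.** Reconcile Sections 7, 8 and 9d and Tables 8A and 8B so that what patients experience up to the 6M questionnaires is the same in both arms:

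- In the randomised phase, tie both the real and the mock measurement to the same 3M visit (±3 weeks), where both arms already have an endoscopy.
- Keep the 3-9 month window only for crossover patients, who are already unblinded.
- If an active patient's real measurement has to be deferred, do a mock at 3M and the real one only after the 6M questionnaires and disclosure.

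The cost is amended wording in those sections and tables, less scheduling flexibility, and some missing exploratory EndoFLIP readings. Deferred patients may also need a separate examination, because Table 8A has no endoscopy at 6M and only an optional one at 12M. For the same reason, moving every follow-up measurement past 6M would cost more than matching the arms at 3M. The sample size and the primary analysis do not change.
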